7.2 Device Complaints

Potential complaints associated with the study investigational devices will be summarized.

Table 8: Summary of Device Complaints

Device Complaint Type	Number of Complaints
Complaint type 1	X
Complaint type 2	X
Complaint type 3	X

7.3 Remote Pain Assessments

As described in Table 1, remote pain assessments are recorded daily by the subject using the CamNtech PRO-Diary Watch and paper-based Subject Diary. The remotely assessed NRS scores for overall pain collected from the PRO-Diary Watch and Subject Diary may be combined and compared to the In-Office assessments to evaluate the consistency across the in-office and remote data collection settings, and supplement the primary and secondary endpoints.

7.3.1 Remote NRS Data Processing Steps

Data from the PRO-Diary Watch data files will be combined with data manually transcribed from the Subject Diary by sponsor personnel. When available, the NRS score recorded on the watch will be the primary source used for analysis of the remote assessments. Paper-based subject diary NRS scores will be used when the watch data is unavailable.

7.3.2 Data Structure

A data file with the combined watch and transcribed paper diary NRS scores will be constructed from the raw data files from the EDC, and archived. The combined file will be formatted as follows:

- Column 1: Subjects (e.g. '001-001')
- Column 2: Dates (format 'MM/DD/YYYY')
- Column 3: Data (NRS values range 0-10, note some values are not integers due to the averaging of watch data)

7.3.3 Calculation of 2-day pain score for comparison between investigational therapy and commercial trial

The remote NRS scores in the combined file may be used to compute a two-day pain score. The two-day pain score will be defined as the second lowest pain score which was achieved by the therapy (equal to the minimum if the minimum occurs more than once). This metric is preferred over the minimum score because it reduces the effect of random factors resulting in a minimum pain score that is a statistical outlier. The two-day pain score will be used to evaluate the performance of the therapy in the commercial trial phase and the investigational phase relative to baseline. The baseline pain score (Phase 1) is the overall NRS score collected at the study enrollment visit. It is not computed from the remote NRS scores.

BENEFIT-02 Study Statistical Analysis Plan

[figure not shown]
The integrated pain score data from the watch and paper diary may be separated into phases:

- Phase II: Commercial Trial
 - Inclusive dates: date of trial lead implant through the date of office visit 1 (randomization)
- Phase III: Investigational Therapy
 - Inclusive dates: (Randomization date + 3 days) until the end of the study period (office visit 3 = study exit).
- Additional notes:
 - Randomization arms in the investigational therapy phase are combined (both A and B)

In order to calculate 2-day pain scores in the commercial trial phase and investigational phase, at least 2 data points (2 test days with recordings) will be required in each phase. Otherwise, the subject will be excluded from the analysis.

The daily pain scores in Phases II and III will be sorted in ascending order. Then, the second value (2-day pain score) will be obtained for both the commercial trial phase and investigational phase. Figure 5 provides an overview of this process.

Figure 5: Flow Chart for Calculation of 2-day Pain Score

7.3.4 Calculation of 2-day pain score for comparison between investigational therapies A and B

For comparisons of remote assessment data between investigational therapies A and B the two-day pain score is calculated as described in Section 7.3.3 with the following exceptions:

- A 2-day pain score for the Commercial Trial Phase is not computed
- The 2-day pain score is only computed from remotely collected NRS values on days prior to cross-over (if it occurs). Specifically, all NRS scores on days following the initial cross-over will be excluded. Note: The Titration Procedures Therapy Block Re-Assigned variable recorded in EDC will be used to verify cross-over (e.g. therapy switches from A to B or from B to A). Examples of cross-over patterns are provided by Table 9.

Table 9: Example Therapy Cross-over of Randomized Subjects

Date	Initial Therapy	Final Therapy	Block Re-Assigned	NRS included?
24-Oct-2019	A	A	unchecked	Yes
25-Oct-2019	A	B	checked	Yes
26-Oct-2019	B	B	unchecked	No
27-Oct-2019	B	A	checked	No
28-Oct-2019	A	A	unchecked	No

7.3.5 Data Validation for Combined Remote Pain Assessment Data Set and 2-day Pain Score

In order to validate the calculation process of the 2-day pain score, 2 SCS experts will develop programs to calculate 2-day pain scores independently. The results obtained for every subject will be compared. Prior to analysis, it will be confirmed that both independent analysis programs generate the same 2-day pain score results, indicating that the calculation processes are correct and the data is accurate. The same process will be used to validate the Pro-Diary Watch and Merged Pro-Diary/Subject Diary datasets. The values contained within the transcribed Paper Diary will also be cross-validated by sponsor personnel, with a minimum of a random 10% sample reviewed for accuracy, with any discrepancies verified, and corrected prior to final analysis.

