5 SAMPLE SIZE ANALYSIS

The BENEFIT-02 Study is designed to limit the number of subjects involved and the duration of intervention, while ensuring sufficient preliminary data regarding the effectiveness and safety of the study SCS therapies is collected in order to accomplish the study objectives.

Since the effect size of each study SCS therapy on the primary outcome measure (NRS for overall pain) is unknown, statistically driven sample size estimation is not possible. A reduction of approximately two points on an NRS for chronic pain represents a clinically relevant difference.¹

In order to detect a difference of approximately two in mean change in NRS pain score (from baseline to the final study visit) between the two study SCS therapies, a target of 70 subjects should complete the 12 day study stimulation period (~35 subjects for each study SCS therapy).

Therefore, to account for expected attrition due to subject withdrawal following consent but prior to completion of the study testing period:

- Up to 226 subjects will be provisionally enrolled
 - Assumed 51% drop out rate between consent and the randomization visit (e.g. failed commercial trial, withdrawn consent, etc.)
- Approximately 110 subjects will undergo randomization (fully enrolled)
 - Assumed 15% drop out rate following randomization prior to initiation of the assigned study SCS therapy (e.g. subject doesn't meet post-washout inclusion criteria)
- Approximately 93 subjects will initiate the randomly assigned study SCS therapy
 - Assumed 25% drop out rate following initiation of the randomly assigned study SCS therapy (e.g. non-compliance with study assessment schedule, withdrawn consent, subject lost to follow-up, etc.)
- Approximately 70 subjects will complete the study testing period

¹ J. T. Farrar *et al.*, "Clinical importance of changes in chronic pain intensity measured on an 11-point numerical pain rating scale," *Pain*, vol. 94, pp. 149-158, Nov 2001.

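### The two-day pain score depends on how many days were recorded, so it should not be tested against a single baseline score or between phases with different numbers of days

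*SAP*

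**What the plan says.** SAP 7.3.3 is headed "Calculation of 2-day pain score for comparison between investigational therapy and commercial trial". The definition reads: "The two-day pain score will be defined as the second lowest pain score which was achieved by the therapy". It sorts all daily remote scores in a phase and takes the second value. The only rule on the number of days is "at least 2 data points (2 test days with recordings) will be required in each phase". There is no upper limit, and nothing equalises the count between phases. The stated reason for the choice is protection against an outlying minimum.

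The score is to be "used to evaluate the performance of the therapy in the commercial trial phase and the investigational phase relative to baseline". The comparator is one value: "The baseline pain score (Phase 1) is the overall NRS score collected at the study enrollment visit". The SAP adds that it does not come from the remote scores.

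Phase II runs from the implant date to the randomization visit, both included. Protocol section 2 leaves the conduct of the commercial trial to standard of care, and the supplied text gives no length for it. Phase III is defined as "Inclusive dates: (Randomization date + 3 days) until the end of the study period", and Protocol 1.1 puts the final visit 14 days after randomization.

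SAP sections 7 and 7.4 (Table 11) plan an ANOVA and post hoc paired t-tests across baseline, commercial trial and study phase, with p < 0.05 as significant. Table 11 labels the phase values only as remote assessments. The heading of 7.3.3 is what ties the two-day score to this comparison.

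**The concern.** A second-lowest value is a selected value. The more days it is selected from, and the more the scores vary from day to day, the lower it is expected to be, whatever the therapy does. The baseline score is not selected in this way. A difference between the two therefore mixes the effect of therapy with the effect of picking a low day. A difference between phases mixes it with the difference in recorded days.

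What is at stake is mainly the reported size of improvement. SAP 7.3 says the remote scores may supplement the endpoints, and SAP section 5 supplies a yardstick: "A reduction of approximately two points on an NRS for chronic pain represents a clinically relevant difference". An inflation of about one point would count for a lot on that scale.

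**Working it through.** The plan gives no figure for this score, so there is none to reproduce.

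**Inputs from the documents.** Phase III runs from randomization +3 to +14, so 14 − 3 + 1 = 12 dates. The minimum is 2 recorded days. About 70 subjects complete (SAP section 5). The significance level is 0.05, taken as two-sided.

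**Assumptions.** The within-subject day-to-day SD is not given; 0.5, 1.0 and 1.5 points are shown. The commercial trial length and recording compliance are not given either; 5, 7 and 10 days, and full or 60% recording, are shown.

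**Step 1: expected score.** For n independent normal daily scores with mean μ and SD σ, the expected second-lowest is μ + σ·c(n), where c(n) = ∫ z·n(n−1)·Φ(z)·[1−Φ(z)]^(n−2)·φ(z) dz. Numerical integration gives:

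| n | 2 | 3 | 4 | 5 | 6 | 7 | 8 | 11 | 12 |
|---|---|---|---|---|---|---|---|---|---|
| c(n) | +0.56 | 0.00 | −0.30 | −0.50 | −0.64 | −0.76 | −0.85 | −1.06 | −1.12 |

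Sensitivity at 12 days:
- Day-to-day correlation of 0.5 or 0.8 gives −1.03 or −0.83.
- Skewness of +1 or −1 gives −1.00 or −1.15.

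If home scores run 0.5 SD above office scores, the neutral point moves from 3 days to about 5.

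**Step 2: against baseline.** Shown fall = true fall − σ·c(n). With 12 days and a true fall of 1.0:
- σ = 0.5: 1.0 + 0.5 × 1.116 = 1.56
- σ = 1.0: 1.0 + 1.116 = 2.12
- σ = 1.5: 1.0 + 1.5 × 1.116 = 2.67

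Simulation with scores rounded and capped to 0–10 gives 1.56, 2.10 and 2.65. The mean of the daily scores shows 0.98 to 1.00 in the same settings.

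**Step 3: study minus commercial trial, equal therapies, σ = 1.0.** A D-day trial gives D + 1 Phase II dates. With every day recorded and every date treated as an ordinary therapy day, the expected difference is c(12) − c(D+1):
- D = 5: −1.116 + 0.642 = −0.47
- D = 7: −1.116 + 0.852 = −0.26
- D = 10: −1.116 + 1.062 = −0.05

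Simulations agree to within about 0.01. With 70 subjects the paired t-test rejects in about 100%, 89% and 11% of simulated trials.

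The sign can reverse. With 60% of study days recorded and a 10-day trial, the difference is +0.31, against the study therapy. If the implant-date and randomization-date scores are assumed 2 and 1 points higher, it is about +0.20.

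**Step 4: would equal day counts be enough?** No. With 12 days in both phases the phase comparison is neutral if variability is equal, but each phase still sits 1.12 SD low against baseline. A phase with SD 1.5 would also score lower than one with SD 1.0: −1.67 against −1.12 points.

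**The case against.** The case on the other side has five parts.

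- **Best level achieved is a fair thing to describe**, and the second-lowest is steadier than the minimum. This stands. It supports reporting the score, not testing it against an unselected value.
- **The analyses are optional and the endpoints do not use them.** SAP section 4 reserves in-office data for the endpoints. Table 2 already gives the unselected in-office change, and Table 10 the unselected remote means. This stands and limits the severity. A reader might infer that the primary results are affected; they are not.
- **No true change from baseline is an unrealistic null after a successful commercial trial.** This stands. For the baseline comparison, what matters is the inflated effect size, not a false-positive rate.
- **The size rests on an SD that the documents do not give.** This stands for the size. That the score depends on the day count does not rest on it.
- **Day-number matching assumes that both phases follow a similar time course.** Study therapy is reprogrammed in phone calls up to once a day, while the commercial trial runs independently. This stands, so a matched test can only be an option.

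A reader might also infer that the score is built to favour the study therapy over the commercial trial. The documents do not support that: trial length and recording compliance are not given, and Step 3 shows both signs. Nor does the score always overstate improvement. At the SAP's own 2-day minimum it understates it.

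**Conclusion.** The point holds. When four or more days are recorded and scores are roughly symmetric, the two-day score overstates improvement over the single baseline. With 12 days the excess is about 1.1 within-subject SDs. At an assumed SD of 1.0, that is enough to present a one-point fall as a two-point one. Between phases the score favours the one with more recorded days, in a direction that the supplied text does not settle.

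Skew, day-to-day correlation or an office-to-home shift changes the amount and the neutral day count. They do not remove the dependence on recorded days.

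For therapy A versus B (SAP 7.3.4), dropping days after cross-over raises the score of subjects who crossed over. If 30% of one arm had 4 days instead of 12, that arm's mean would rise by 0.3 × (1.12 − 0.30) ≈ 0.25 SD. With similar cross-over timing in both arms this largely cancels, so it deserves only a remark.

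Severity is minor to should-fix, because these are optional analyses of additional data.

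**What to change.** 1. **Minimum change.** Label the two-day score descriptive, report recorded days per phase beside it, and attach no p-value against baseline or between phases.
2. **Each phase against baseline.** Test the mean of the recorded daily scores in that phase. State that this compares remote with in-office scores, and show Table 10's paired differences beside it.
3. **Study versus commercial trial, if tested.** Use one variable for both the ANOVA and its post hoc test: each subject's mean over the day numbers recorded in both phases. Leave out every date on which therapy starts or stops within the day (implant, randomization and final visit). Unmatched phase means are not enough here. If both therapies improved by 0.15 points a day and the commercial trial lasted 7 days, commercial days 1–6 and study days 1–12 would differ by 0.15 × (6.5 − 3.5) = 0.45 points with equal therapies (0.15 × (6.0 − 3.5) = 0.375 once the final-visit date is dropped). State that matching assumes a similar time course in both phases and does not use later study days. If that is not acceptable, report the phase comparison descriptively without a p-value.
4. **SAP 7.3.4.** Note only that truncation at cross-over makes the score depend on cross-over timing.

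**Cost.** Item 1 is SAP text plus a day count. Items 2 and 3 need new per-phase variables from the existing combined file, in both validation programs (SAP 7.3.5). The reported improvement over baseline will probably be smaller, and a mean no longer answers what the best score achieved was. Matching also loses subjects who have no common day. With 60% random recording in both phases, a day number is shared with probability 0.6 × 0.6 = 0.36. About 70 × (1 − 0.64^k) subjects then remain, where k = D − 1 is the number of full commercial-trial days: 58, 65 and 69 for trials of 5, 7 and 10 days.

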7.3.6 Remote Pain Assessments Example Tables and Figures

Table 10: NRS Score Source Comparison

Overall NRS	Baseline/Enrollment (n=XX/XX)	Trial End/Rand (n=XX)	Midpoint Evaluation (Study OV2) (n=XX)	Study Exit (n=XX)
Mean In-Office Assessment \pm SEM	X.X \pm X.XX	X.X \pm X.XX	X.X \pm X.XX	X.X \pm X.XX
Mean Remote Assessment \pm SEM	X.X	X.X \pm X.XX	X.X \pm X.XX	X.X \pm X.XX
Paired T-Test	-----	X.XX	X.XX	X.XX

[figure not shown]
Figure 6: NRS Score Source Comparison

7.4 Comparison between Commercial Trial and Investigational Study Phase

A comparison between commercial trial and investigational study phase may be completed for the entire sample of subjects with Therapy A and Therapy B combined including any subjects that were re-assigned and/or reprogrammed to the alternative therapy. Only subjects with data available in each study interval will be used to compare across study time points.

Table 11: Overall NRS (Mean \pm SEM, XX Subjects)

Overall NRS	Mean NRS \pm SEM	P-value Baseline vs. (post hoc paired t-test)	P-value Commercial vs. (post hoc paired t-test)
Baseline (In-Office Assessment) (N=XX)	X.X \pm X.XX	-----	-----
Commercial Trial (Remote Assessment) (N=XX)	X.X \pm X.XX	X.XXXXX	-----
BENEFIT-02 Study (Remote Assessment) (N=XX)	X.X \pm X.XX	X.XXXXX	X.XXXXX
Overall NRS P-value (ANOVA)	p = 0.XXX	-----	-----

[figure not shown]
Figure 7: Overall NRS (Mean \pm SEM, XX Subjects)

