1.4 STUDY DATA COLLECTION WATCH

At the enrollment visit, subjects will be provided a CamNtech PRO-Diary study data collection watch (shown in Figure 1) that includes an accelerometer and programmable graphical user interface, and will receive initial training on its usage. The study data collection watch will be utilized throughout the study after the enrollment visit to collect activity metrics continuously and subject reported data from the following scheduled and subject triggered assessments:

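### In SAP Table 11, both baseline contrasts and the ANOVA set one in-office score against second-lowest remote scores, so source and selection are read as therapy effect

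*SAP*

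**What the plan says.** Table 11 in SAP 7.4 has three rows, each labelled with its source:

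- "Baseline (In-Office Assessment) (N=XX"
- "Commercial Trial (Remote Assessment) (N=XX"
- "BENEFIT-02 Study (Remote Assessment) (N=XX"

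Both later rows are tested against baseline by post hoc paired t-test. The study row is also tested against the commercial row, and an ANOVA covers all three.

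SAP 7.3.3 defines the scores for this comparison, with the arms combined as in 7.4. On baseline: "The baseline pain score (Phase 1) is the overall NRS score collected at the study enrollment visit", and "It is not computed from the remote NRS scores". On the phases: "The two-day pain score will be defined as the second lowest pain score which was achieved by the therapy". The stated use is to "evaluate the performance of the therapy in the commercial trial phase and the investigational phase relative to baseline".

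SAP 7 sets p<0.05 as significant for all of these analyses. SAP 7.3 and Table 10 provide for an optional comparison of in-office and remote scores.

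**The concern.** Three things change between the baseline row and the later rows: the setting (clinic or home), the instrument (visit worksheet or watch/diary), and the summary (one unselected score or a selected low one). All three change at the point where stimulation begins, so a paired test against baseline cannot separate them from the effect of stimulation.

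At stake are two p-values and an ANOVA that could be significant with no therapy effect. They would appear in the same report as the in-office change from baseline in Table 2, and the two could differ for reasons unrelated to therapy. The SAP treats agreement between the settings as something to be checked, so Table 11 should not depend on it.

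**Working it through.** The plan states no figure for this comparison, so there is none to reproduce. The check is a reading of the definitions, followed by two illustrations.

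**1. Which contrasts are affected**

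| Contrast in Table 11 | Source | Summary |
|---|---|---|
| Baseline vs commercial trial | in-office vs remote | single score vs second-lowest day |
| Baseline vs study phase | in-office vs remote | single score vs second-lowest day |
| Commercial trial vs study phase | remote vs remote | second-lowest vs second-lowest |
| ANOVA over three rows | mixed | mixed |

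Table 10 plans paired tests between sources at trial end, midpoint and exit. Its baseline column has no test, and no step carries a source difference into Table 11.

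**2. Source offset alone**

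Inputs: N = 70 (completers, SAP 5); alpha 0.05 (SAP 7), two-sided assumed; offset d and SD of the paired difference s assumed, because the documents give neither. With no therapy effect, the paired t statistic is noncentral t with 69 degrees of freedom and noncentrality d × √70 / s, where √70 = 8.37. For d = 0.5:

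- s = 1.5: 0.5 × 8.37 / 1.5 = 2.79, rejection rate 79%
- s = 2.0: 0.5 × 8.37 / 2.0 = 2.09, rejection rate 54%
- s = 2.5: 0.5 × 8.37 / 2.5 = 1.67, rejection rate 38%

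For d = 0.3 the rates are 38%, 24% and 17%. For d = 0 the rate is 5%. An offset in the opposite direction would hide benefit by the same amount.

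**3. Selection alone**

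Days in the study phase: from randomization + 3 to the final visit at day 14, so 14 − 3 + 1 = 12. The length of the commercial trial is not given in the material reviewed; 6 to 7 days is assumed. For independent normal days, the second-lowest of k values lies below the subject's own mean by:

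- k = 6: 0.64 SD
- k = 7: 0.76 SD
- k = 12: 1.12 SD

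At an assumed daily SD of 1 to 1.5, that is 0.64 to 1.14 points for the commercial trial (0.64 × 1 to 0.76 × 1.5) and 1.12 to 1.67 points for the study phase (1.116 × 1.5 = 1.67).

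A simulation with scores rounded to 0–10 (70 subjects, 6 and 12 days, no offset, no therapy effect) gave the following apparent falls from baseline. P<0.05 occurred in 97% to 100% of trials.

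| Daily SD | 6 trial days | 12 study days |
|---|---|---|
| 0.5 | 0.32 | 0.56 |
| 1.0 | 0.63 | 1.10 |
| 1.5 | 0.92 | 1.63 |

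**4. The two problems are separate**

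In the same simulation, replacing the second-lowest day with the phase mean returns the false-positive rate to about 5% when there is no offset. With a 0.5-point offset it stays at 71% to 100%. Remote scores throughout, still summarised by the second-lowest day, would leave the selection in place. One in-office score at every time point gives 4% to 5% in every contrast, because a constant source offset cancels and nothing is selected.

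**5. What like-for-like data exist**

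Table 10 has in-office overall NRS at enrolment, trial end/randomization, midpoint and exit, so the in-office series is complete by design. A remote baseline is less certain. Protocol 1.4 says "The study data collection watch will be utilized throughout the study after the enrollment visit", but SAP 6.1.1 allows baseline to be taken on the implant date and Phase II begins on that date. Table 10 shows the remote baseline cell without SEM or test.

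**The case against.** The case for leaving Table 11 alone has real weight. The analysis is optional, supplementary and part of a feasibility study. Table 11 labels its sources openly. The section's own question, commercial trial against study phase, is remote against remote. Like-for-like in-office results are largely planned already: baseline against final visit in Table 2, Visit 1 against Visit 3 in Table 5, and in-office means at all time points in Table 10.

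All of this stands, and it limits the weight of the point. It does not answer it. The baseline p-values and the ANOVA would still be reported, and a label does not correct them. Tables 2 and 5 exclude re-assigned subjects and give no test of baseline against Visit 1. Table 10's check is optional and adjusts nothing.

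Four stronger readings are tempting and are not supported:

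- **The main efficacy results are biased in this way.** They are not: SAP 4 bases the primary and secondary endpoints on in-office data.
- **Remote scores run lower, so therapy is favoured by the source change.** The documents give neither size nor direction for an offset.
- **The artefact is close to the two-point relevant change in SAP 5.** Only the upper corner comes near (1.67 points: 12 days, SD 1.5). At 6 days and SD 1 it is 0.64, about a third of two points. These figures measure the second-lowest rule, not the source mismatch.
- **Wearing the watch from enrolment guarantees a remote baseline.** Subjects whose baseline falls on the implant date would have no pre-implant watch scores.

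**Conclusion.** The point holds for the two baseline contrasts and the ANOVA in Table 11, and for nothing beyond them as far as source is concerned. That follows from the definitions and needs no assumption. Any in-office/remote offset passes in full into both baseline contrasts, and selection of a low day is added to it.

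The sizes are illustrative. The 38% to 79% false-positive range rests on an assumed 0.5-point offset and paired SDs of 2.5 to 1.5. The selection figures, about 0.6 to 0.8 SD for the commercial trial and about 1.1 SD for the study phase, assume independent days, and the first also assumes 6 to 7 trial days. Correlated days or few recordings shrink them. At the permitted minimum of two recordings the second-lowest is the higher score, and the direction reverses (+0.56 SD).

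The commercial-versus-study contrast has no source mismatch, but unequal numbers of days still affect it through the second-lowest rule: 0.24 to 0.71 points in the simulation with 6 against 12 days. This is a worthwhile correction to a supplementary analysis.

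**What to change.** In SAP 7.4 and Table 11:

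- Base both baseline contrasts and the ANOVA on in-office overall NRS at enrolment, Visit 1 and Visit 3, for all subjects with data at the three points, including re-assigned subjects.
- Keep remote scores only for commercial trial against study phase, and summarise each phase by its mean rather than its second-lowest day.
- Do not rely on a remote baseline, which may be missing for many subjects.

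The cost is SAP wording; the data are already planned. The in-office rows would partly repeat Tables 2, 5 and 10, and each rests on one visit score, so it is noisier than a phase mean. The change removes the two artefacts described here; a before-after contrast with both arms combined still has no control group.
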